12.2.2.6 Additional Information Concerning RECIST v1.1

Full details concerning the use of RECIST v.1.1 may be found in the full article by Eisenhauer et al. (2009), which is attached as Appendix B.

12.3 Evaluable patients

12.3.1 Safety Population

Patients who received any dose of the study drug.

12.3.2 MTD/RP2D Determination Population during Phase 1b portion

The population evaluable for MTD/RP2D determination will consist of all patients who received at least 75% of the planned Debio 1347 dose during the DLT period (Day 1 to Day 28 of Cycle 1 and assessments prior to drug administration on C2D1). Patients who experienced a DLT will be included in the MTD/RP2D determination population regardless of the dose of Debio 1347 received.

Patients who fulfill any of the following situations will be excluded from the MTD/RP2D determination population:

1. Administration during the DLT period of non-permitted concomitant treatments with impact on DLT evaluation.
2. Proper DLT/safety evaluation is judged to be difficult because of protocol violation(s).

12.3.3 Efficacy population

Patients who have measurable and/or non-measurable disease, according to RECIST version 1.1. criteria, undergo a baseline disease assessment, at least one on-treatment assessment, but excluding those who fulfill any of the following conditions:

1. Violation of clinically relevant inclusion/exclusion criteria.
2. Administration of non-permitted concomitant treatments.

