9.5 Subject replacement strategy

- Patients not eligible for the MTD/RP2D determination of the phase 1b portion will be replaced (see section 12.3.3)
- Patients not eligible for efficacy evaluation for the Phase II portion of the study will also be replaced

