- f) Calcium regulating hormone assessments (whole-PTH, 1,25(OH) 2D, PTHrP) will be performed every cycle until Cycle 3 and every 3 cycles thereafter.
- g) Ophthalmological tests to be repeated as clinically indicated during treatment. Complete ophthalmologic examinations will be performed at screening and, as soon as clinically indicated, if a patient reports any visual abnormality. Complete ophthalmologic examination will be performed and interpreted by a qualified ophthalmologist, including visual acuity testing, slit-lamp ophthalmoscopy and indirect ophthalmoscopy. At the final visit and 28 days after the last dose, slit-lamp ophthalmoscopy will be performed.
- h) Tumor assessments (patients with a history of brain mets will be required to have brain CT scans with contrast or MRIs) to be performed every 8 weeks for 48 weeks (i.e. cycle 2, 4, 6 between days 22 and 28) and then every 12 weeks thereafter (i.e. cycle 9, 12, 15 again between days 22 and 28 etc.).
- i) Plasma samples for cfDNA analysis will be collected prior to dosing on cycle 1, cycle 1 day 15, day 1 of C3 and then at EOT.
- j) Plasma samples for PK will be collected both during phase 1 and 2. Phase 1 PK will be collected prior to dosing on day 1 and 15 of cycle 1 and then day 1 of each cycle thereafter. Phase 2 PK will be collected prior to dosing on day 15 of cycle 1 and day 1 of cycle 2.

k) Baseline tumor biopsies will be obtained during screening for all patients enrolled in the study, at least three fragments on a core biopsy

l) Documented negative tests prior to screening period is acceptable.

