14.0 BIOSTATISTICS

Phase I: The phase I portion of this trial will evaluate 2 dose cohorts including 1 de-escalation cohort (N= minimum 4 and maximum 12) as shown in the table below. Only the dose of Debio 1347 will be de-escalated. There will be no intra-patient dose escalation. 1 cycle = 28 days.

The Dose Limiting Toxicity (DLT) observation period includes Day 1 to Day 28 of Cycle 1, plus the assessments prior to drug administration on Cycle 2, Day1.

Cohort/Dose level	Debio 1347	Fulvestrant
-1	60mg	500mg IM
1 (Starting dose cohort)	80mg	500mg IM

If none or one of the initial 3 patients in dose level 1 has DLT, 3 additional patients will be treated at the same dose level. If 2 or more patients experience DLT at this dose level, then dose level -1 will be evaluated. Should 2 or more patients experience DLT at dose level -1, the study will stop accrual. If only 1 of the 3 initial patients experiences a DLT at dose level -1, 3 additional patients will be evaluated at this dose level. Patients who withdraw before completing a full cycle of treatment for reasons other than development of a DLT will be replaced.

Selected non-hematologic and hematologic toxicities, as measured by the NCI CTCAE Version 4.0, will be described by frequency and grade, by cycle and over all cycles, with the maximum grade over all cycles used as the summary measure per patient. In a descriptive secondary analysis, clinical benefit rate will be estimated by dose.

We anticipate accruing 1-2 patients/month in the phase 1b portion of the study.

Phase II: The purpose of the phase II portion of the study is to evaluate the efficacy of this regimen, using the MTD/RP2D as determined in the Phase Ib part of the trial. Efficacy will be measured by the clinical benefit rate: proportion of patients who have a best overall response

of a complete response, a partial response, or stable disease (SD) for at least 24 weeks (SD \geq 24 weeks) i.e. (CR+PR+SD \geq 24 weeks). In the PALOMA-3 trial where ER+ MBC patients were randomized to fulvestrant plus palbociclib versus fulvestrant, the CBR (ORR + SD $>$ 24 weeks) was 34% (95% CI, 29.0 to 39.3) vs 19% (95% CI, 13.4 to 25.6). There is no historic data available for patients who have progressed on palbociclib. Since this trial will allow patients who have received prior palbociclib, it was decided that a target clinical benefit rate below 10% will not be worthy of further consideration and a response rate of 25% will be considered promising.

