Simon's two-stage optimal design will be used to study the treatment efficacy since it permits early termination of the study. We will allow early termination only if the data at the first stage indicate that the treatment is highly inactive. 18 patients will initially enter the study. If there are 2 or fewer patients with clinical benefit (CR, PR or SD \geq 24) observed, the study will be terminated early and declared to have a negative result. If 3 or more patients have clinical benefit, enrollment will be extended to 43 patients. Note, we will halt the trial after the first stage while awaiting results from the first 18 patients.

If 8 or more patients with clinical benefit are observed among the 43 patients, the study will be considered to have a positive result and this regimen would be considered worthy of further testing in this disease. The probability of early termination is 0.73 if the true clinical benefit probability is \leq 10%. This design would effectively discriminate between true clinical benefit rates of \leq 10% and \geq 25%. This design has 80% power and a type I error of 5%.

Upon completion of the study, the true clinical benefit rate will be estimated via the observed rate and an exact confidence interval will be constructed.

The maximum of 43 patients requires about 2 years of patient accrual with an anticipated enrollment of 1-2 patients per month.

In secondary analyses for the Phase Ib portion of the trial, the ORR will be summarized as a proportion with a 95% exact confidence interval. TTP, PFS and OS will be evaluated using Kaplan-Meier methods. All toxicities as measured by the NCI CTCAE Version 4.0, will be described by frequency and grade, by cycle and over all cycles, with the maximum grade over all cycles used as the summary measure per patient. All patients will be included in the safety analyses regardless of whether a patient is not evaluable for the efficacy endpoint.

All exploratory analyses will be conducted for each phase of the trial separately. PK/PD measures such as AUC, Cmax, and Cmin will be calculated and summarized. Exploratory endpoints that aim to investigate biomarkers of clinical benefit and/or resistance will be evaluated descriptively and graphically. If there are a sufficient number of clinical benefit events, nonparametric tests (Fisher's exact or Wilcoxon rank sum) will be used to test the exploratory hypotheses depending on the distribution of the biomarker.

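### Sections 12.3.3 and 9.5 let treated Phase II patients with no on-treatment assessment be dropped and replaced, and Section 14 names no analysis set for the clinical benefit rate

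*Combined protocol and SAP*

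**What the plan says.** Section 12.3.3 defines the efficacy population as patients with measurable or non-measurable disease who "undergo a baseline disease assessment, at least one on-treatment assessment, but excluding those who fulfill any of the following conditions". The two conditions are a clinically relevant eligibility violation and use of non-permitted concomitant treatment. It is the only efficacy population in the document.

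Section 9.5 adds: "Patients not eligible for efficacy evaluation for the Phase II portion of the study will also be replaced". This bullet does not cite 12.3.3, but no other definition is available for it to refer to.

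Section 14.0 defines CBR as the proportion of patients whose best response is CR, PR or stable disease for at least 24 weeks. For stage 1 it says "18 patients will initially enter the study"; 2 or fewer benefits stop the trial. The final criterion is "If 8 or more patients with clinical benefit are observed among the 43 patients". The section claims 80% power and 5% type I error. Of the null it says "it was decided that a target clinical benefit rate below 10% will not be worthy of further consideration", without saying whether that rate is among treated or evaluable patients. It does expect some unevaluable patients, since it keeps everyone in the safety analyses "regardless of whether a patient is not evaluable for the efficacy endpoint". It gives no matching rule for the CBR count.

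Footnote h to the Section 10.1 schedule sets tumor assessments "to be performed every 8 weeks for 48 weeks (i.e. cycle 2, 4, 6 between days 22 and 28", so the first scheduled scan falls at about week 8.

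**The concern.** Membership of the efficacy population depends on something that happens after treatment starts. A patient who dies or leaves before the first scan has had treatment without known benefit, yet under 12.3.3 and 9.5 that patient can be removed and another enrolled in the same slot. Section 12.2.2.4 makes a missing assessment not evaluable, and nothing states outright that a treated, never-assessed patient counts as a non-benefit.

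The 3/18 and 8/43 rule is the only go/no-go test in Phase II. If the patients removed are mainly failures, both the reported CBR and the chance of passing the rule rise relative to all treated patients. More than 43 patients may also be treated, which Section 14.0 does not reflect.

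**Working it through.** **Inputs from Section 14.0.** Stage 1: 18 patients, stop at 2 or fewer benefits. Total 43 (25 in stage 2), positive at 8 or more. Null rate 10%, promising rate 25%.

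**Step 1: reproduce the plan's figures.** With X1 ~ Bin(18, p) and X2 ~ Bin(25, p):

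- P(early stop) = P(X1 ≤ 2)
- P(positive) = sum over x = 3,…,18 of P(X1 = x) × P(X2 ≥ 8 − x)

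| p | P(early stop) | P(positive) |
|---|---|---|
| 0.10 | 0.734 | 0.0480 |
| 0.25 | 0.135 | 0.8003 |

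These match the stated 0.73, 5% and 80%. The design is computed correctly.

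**Step 2: effect of dropping and replacing.** The documents give no loss rate, so two quantities are assumed. Let d be the share of treated patients with no qualifying assessment, and f the fraction of those losses that are certain failures, the rest being lost at random. If the CBR among treated patients is 10%, the rate among the evaluable patients who fill the 18 and 43 places is

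p = 0.10 / (1 − d × f).

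Putting p into the Step 1 formulas:

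| Assumption | p among evaluable | P(early stop) | P(positive) |
|---|---|---|---|
| Loss unrelated to benefit (f = 0), any d | 0.1000 | 0.734 | 0.0480 |
| f = 0.5, d = 5% | 0.10/0.975 = 0.1026 | 0.721 | 0.0543 |
| f = 0.5, d = 10% | 0.10/0.95 = 0.1053 | 0.707 | 0.0614 |
| f = 1, 1 of 44 replaced | 0.10 × 44/43 = 0.1023 | 0.722 | 0.0537 |
| f = 1, d = 5% | 0.10/0.95 = 0.1053 | 0.707 | 0.0614 |
| f = 1, d = 10% | 0.10/0.90 = 0.1111 | 0.677 | 0.0787 |

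Because the attained error is already 4.8%, there is little slack: with f = 1, 5% is passed at a loss of about 0.8%.

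**Step 3: number treated.** Filling 43 evaluable places takes 43/0.95 = 45.3, so 46 treated patients at d = 5%, and 43/0.90 = 47.8, so 48 at d = 10%.

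**Step 4: the alternative rule.** Apply 3/18 and 8/43 to the first 18 and first 43 treated patients, with unassessed patients counted as non-benefit. If 10% and 25% are rates among treated patients, error is 0.0480 and power 0.8003 whatever d is. If they were meant as rates among evaluable patients and all losses are failures, the treated rates are lower by the factor (1 − d):

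| d | Null rate | Error | Promising rate | Power |
|---|---|---|---|---|
| 5% | 0.10 × 0.95 = 0.095 | 0.0373 | 0.25 × 0.95 = 0.2375 | 0.753 |
| 10% | 0.10 × 0.90 = 0.090 | 0.0283 | 0.25 × 0.90 = 0.225 | 0.697 |

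**The case against.** **The plan's 5% is not wrong.** A reader might infer that the type I error is misstated or demonstrably inflated. The documents do not support that. Section 14.0 claims 5% for the 18/43 design, which Step 1 confirms. Section 12.3.3 sits under a heading on evaluable patients, and a natural reading makes it the CBR set, with 10% and 25% as evaluable-set rates; on that reading there is no inflation. This stands, and any excess is conditional on the other reading.

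**Section 14.0 may already count everyone.** Taken literally, patients who enter and have no qualifying response are non-benefits. That is arguable, but it then contradicts the replacement rule in 9.5. On either reading the CBR set is not fixed.

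**Few patients should be lost.** This stands in large part. Section 6.2 requires ECOG 0–1 and life expectancy above 3 months. Section 9.4 lets patients who stop Debio 1347 for toxicity stay on study with fulvestrant. Section 10.1 makes the end-of-treatment visit mandatory. Section 12.2.2.4.1 calls for scans when progression is suspected and for efforts to document progression after stopping. Section 13.1 follows patients who stop without progression for disease status. What remains is early death, withdrawal of consent (after which 13.1 allows no further observation) and loss to follow-up. To these may be added patients whose only assessment is at the end-of-treatment visit, 2–4 weeks after the last dose, because the plan does not say whether that is on-treatment. Section 12.2.2.4.1 also gives a scan interval of 3 cycles, against 8 weeks in footnote h; the two must be reconciled, and the longer interval would widen the window for loss.

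**An evaluable set with replacement was chosen in advance.** True, and keeping patients later found ineligible in the primary denominator of a biomarker-selected trial is debatable. That argues for stating how such patients are handled; it does not justify dropping early failures.

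**Conclusion.** The concern holds in a limited form: as written, the rules allow treated patients with no assessment to be removed and replaced, and this pushes the CBR and the go/no-go decision upward relative to all treated patients. The type I error claim is correct for the design and for evaluable patients; it is not shown for treated patients.

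The 5.4% to 7.9% range rests on reading 10% as a treated-patient rate, on an assumed loss of 1 in 44 up to 10%, and on every loss being a failure. With half the losses failures it is 5.4% (5% lost) or 6.1% (10% lost). Given the provisions that limit loss, the likely effect is small. Severity is minor to moderate.

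One neighbouring matter should not be read as support for this point. Section 9.1.2 lists phosphorus absorbers as excluded while Section 9.4.3 directs phosphate binders, so condition 2 of 12.3.3 read literally could exclude patients treated as the protocol directs. That is a separate inconsistency, and those sections must be reconciled.

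**What to change.** - **Section 14.0:** name the primary CBR set as all Phase II patients who received study treatment, state that 10% and 25% refer to that set, and count patients with no post-baseline tumor assessment as having no clinical benefit. Apply 3/18 and 8/43 to the first 18 and first 43 treated patients.
- **Section 9.5:** do not replace treated patients for lack of an on-treatment assessment.
- **Section 12.3.3:** keep this set as a sensitivity analysis. State in advance how treated patients who meet condition 1 or 2 are handled, without letting exclusion depend on outcome.

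The change is to wording and adds no patients to the planned 43. The reported CBR will be slightly lower: with one loss among 44 treated, 8/44 = 18.2% rather than 8/43 = 18.6%. If the sponsor meant 10% and 25% for evaluable patients and all losses are failures, the test becomes stricter, with error 3.7% and power 75% at 5% lost, or 2.8% and 70% at 10% lost. Recovering 80% power would then need more patients. The plan should acknowledge this.

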2.1 OBJECTIVES AND SCIENTIFIC AIMS

Primary Objectives:

Phase 1:

- To determine the safety, tolerability, maximum tolerated dose (MTD)/recommended phase 2 dose (RP2D) of Debio 1347 Plus Fulvestrant in patients with ER+/HER2-/FGFR amplified metastatic breast cancer

Phase 2:

- To investigate the anti-tumor activity of Debio 1347 in combination with fulvestrant in patients with ER+/HER2-/FGFR-amplified metastatic breast cancer as defined as clinical benefit rate (CBR: Objective Response Rate plus Stable disease \geq 24 weeks)

Secondary objectives:

Phase 1:

- To obtain a preliminary assessment of the anti-tumor activity (CBR and overall response rate (ORR)) of Debio 1347 in combination with fulvestrant in patients with ER+/HER2-/FGFR-amplified metastatic breast cancer

Phase 2:

- To further characterize the safety and tolerability of Debio 1347 in combination with fulvestrant in patients with ER+/HER2-/FGFR- amplified metastatic breast cancer
- To determine the overall response rate (ORR), time to progression (TTP), progression-free survival (PFS) and overall survival (OS) for the combination of Debio 1347 with fulvestrant in patients with ER+/HER2-/FGFR- amplified metastatic breast cancer

Exploratory Objectives:

Phase 1 and Phase 2:

- To measure the pharmacokinetic (PK) parameters of Debio 1347 in combination with fulvestrant
- To measure pharmacodynamic biomarkers of FGFR inhibition
- To make an assessment of biomarkers of response and/or resistance from archival tissue and fresh tumor biopsies (using next generation sequencing, FISH, protein and mRNA expression) and plasma (cell-free DNA) and correlate with clinical benefit

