9.1 Concomitant Medications

Administration of concomitant when administered between the date of informed consent signature and the last visit (including follow-up) will be recorded.

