9.1.2 Excluded Concomitant Medications

Subjects must be instructed not to take any medications, including over-the-counter products, without first consulting with the investigator.

The following medications are considered exclusionary during the study. The Principal Investigator must be notified if a subject receives any of these during the study.

- Any investigational anticancer therapy.

- Any concurrent chemotherapy, immunotherapy, or biologic therapy. Note: concurrent use of bone-directed therapies (such as bisphosphonates or denosumab) is permitted.
- Other antineoplastic agents are prohibited except GnHR agonists and GnHR antagonists for premenopausal women.
- Concurrent use of hormones for non-cancer-related conditions (e.g., insulin for diabetes) is acceptable.
- Immunosuppressive medications including, but not limited to systemic corticosteroids (>10 mg/day prednisone or equivalent), methotrexate, azathioprine, and tumor necrosis factor alpha (TNF- α) blockers. \ In addition, use of inhaled and intranasal corticosteroids is permitted.
- Fibroblast growth factors injections, cosmetics containing FGF.
- High dose systemic steroids, calcitonin preparations, active Vitamin D3 preparations, estrogen preparations, selective estrogen receptor modulators, Vitamin K2 preparations, parathyroid hormones, phosphorus absorbers

In nonclinical studies, Debio 1347 has been seen to affect the cornea. Since corneal disorders may occur when contact lenses are being worn, and the use of Debio 1347 may exacerbate these symptoms, caution should be exercised when using Debio 1347 in a patient wearing contact lenses, and the patient should be monitored.

Although the possibility of Debio 1347 affecting cardiac function in nonclinical studies is low, caution should be exercised when using Debio 1347 with drugs with a known risk of QTc prolongation (see Arizona CERT database at website <http://www.crediblemeds.org/>).

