The hepatic oxidative metabolism of Debio 1347 has been shown in vitro to be mainly mediated by CYP 4F3b, with no or only minor contribution of other metabolic enzymes. Furthermore, according to bi-directional permeability experiments in Caco-2 cells, Debio 1347 is not a substrate of P-glycoprotein (P-gp) or breast cancer resistance protein (BCRP) efflux transporters. Therefore, based on current knowledge, Debio 1347 appears to have a low risk of being victim of PK interaction from other drugs. In contrast, as per in vitro results available so far and Debio 1347 plasma exposure achieved in patients, Debio 1347 is considered at possible risk of perpetrating drug-drug interactions through CYP3A inhibition, CYP3A induction (some transporters such as P-gp might also be co-induced), CYP1A2 repression, or inhibition of several transporters (P-gp, BCRP, multidrug and toxin extrusion protein 1 [MATE1], organic cation transporter 2 [OCT2]; bile salt export pump [BSEP] is also inhibited).

The clinical impact of these in vitro observations is not known. While patients are not precluded from receiving any drugs based upon the potential for a PK drug interaction, patients who are taking concurrent drugs that are known substrates of either CYP3A, CYP1A2, P-gp, BCRP, MATE1 or OCT2 should be carefully monitored.

Notably, due to the irreversible nature of CYP3A inhibition by Debio 1347 and also its in vitro potential for enzyme induction, it should be noticed that the potential for drug-drug

interactions with CYP3A substrates (and possibly also with P-gp substrates) is time-dependent; it may increase with time as patients continue to take Debio 1347, and it may persist for some days after Debio 1347 discontinuation.

A list of drugs that are sensitive or narrow-therapeutic-range substrates of CYP3A, CYP1A2, and substrates of P-gp, BCRP, MATE1 or OCT2 can be consulted in:

- Flockhart DA. Drug Interactions: Cytochrome P450 Drug Interaction Table. Indiana University School of Medicine (2007): <http://medicine.iupui.edu/clinpharm/ddis/table.aspx>, and
- <http://www.fda.gov/Drugs/DevelopmentApprovalProcess/DevelopmentResources/DrugInteractionsLabeling/ucm093664.htm>

If treatment with a prohibited medication is necessary, the patient will be withdrawn from the study.

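### Section 12.3.3 excludes, and 9.5 replaces, patients given any non-permitted treatment, with no time or impact limit, so the stated error rates for the clinical benefit rate are not assured

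*Combined protocol and SAP*

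**What the plan says.** Section 12.3.3 defines the efficacy population as patients with RECIST-assessable disease, a baseline assessment and at least one on-treatment assessment. Its second exclusion reads in full: "Administration of non-permitted concomitant treatments". The parallel exclusion in 12.3.2, for the population used to determine the MTD/RP2D, is limited in both time and relevance: "Administration during the DLT period of non-permitted concomitant treatments with impact on DLT evaluation".

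The prohibition runs throughout the trial. Section 9.1.2 says "The following medications are considered exclusionary during the study", and its list includes other antineoplastic agents, high-dose systemic steroids and systemic corticosteroids above 10 mg/day prednisone equivalent. Section 9.1 (Concomitant Medications) sets the recording window: "Administration of concomitant when administered between the date of informed consent signature and the last visit (including follow-up) will be recorded". Section 9.1.2 adds: "If treatment with a prohibited medication is necessary, the patient will be withdrawn from the study".

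On replacement, 9.5 says "Patients not eligible for efficacy evaluation for the Phase II portion of the study will also be replaced".

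Section 14 sets the decision rule. The trial stops if 2 or fewer of 18 patients have benefit, and is positive if 8 or more of 43 do. It names no analysis set for the CBR. It does say that safety analyses include all patients, even those who cannot be evaluated for efficacy, which implies that the efficacy analysis may leave some out.

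**The concern.** The rule reaches patients who have been scanned on treatment and whose outcome may be known. Receipt of a prohibited drug is a post-baseline event that can be linked to that outcome in two opposing ways.

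- **Deletion of patients without benefit.** A patient who is worsening, but has no documented progression yet, may be given high-dose steroids or another anticancer agent. Under 12.3.3 and 9.5 that patient is replaced and not counted as a failure. This raises the analysed CBR and the type I error.
- **Deletion of patients with benefit.** Treatment continues until progression or unacceptable toxicity, so patients with benefit stay longer and have more time in which to receive a prohibited drug. This lowers the analysed CBR and the power.

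The phase 2 objective is "To investigate the anti-tumor activity of Debio 1347 in combination with fulvestrant in patients with ER+/HER2-/FGFR-amplified metastatic breast cancer as defined as clinical benefit rate". The set left by 12.3.3 describes benefit among patients who received no prohibited drug, which is a different quantity. The 3-of-18 and 8-of-43 boundaries are calibrated for patients who are not removed according to how they fared.

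**Working it through.** **Inputs from section 14.** Null CBR 10%, target CBR 25%; n1 = 18, continue with 3 or more; n = 43, positive with 8 or more; stated power 80%, type I error 5%, early termination 0.73.

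**Step 1: reproduce the design.** With b the binomial probability,

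P(positive | p) = sum over x = 3 to 18 of b(x; 18, p) × P[Bin(25, p) ≥ 8 − x].

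- p = 0.10: early termination 0.734, P(positive) = 0.048.
- p = 0.25: P(positive) = 0.800.

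The plan's figures are correct. The gap between 4.8% and 5% is the usual discreteness of such a design.

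**Step 2: effect of deletion with replacement.** Let s_b and s_n be the shares of patients with and without benefit who are kept. The CBR in the analysed set is

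p' = p·s_b / [p·s_b + (1 − p)·s_n],

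and p' goes through the formula in step 1. The documents give no rate of prohibited-drug use, so every s_b and s_n below is an assumption.

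**Step 3: only patients without benefit deleted (true CBR 10%, s_b = 1).**

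| Share of them deleted | p' | Type I error |
|---|---|---|
| 10% | 0.10/(0.10 + 0.90×0.90) = 11.0% | 7.5% |
| 15% | 0.10/(0.10 + 0.90×0.85) = 11.6% | 9.4% |
| 20% | 0.10/(0.10 + 0.90×0.80) = 12.2% | 11.8% |

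**Step 4: deletion driven by time on study (true CBR 25%).** Assume a chance q of prohibited use per 12 weeks. Patients without benefit are on study for 12 weeks, so s_n = 1 − q. Patients with benefit are on study for 36 to 72 weeks, so s_b = (1 − q)^k with k = 3 to 6.

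| q | k | s_b | p' | Power |
|---|---|---|---|---|
| 2% | 3 | 0.941 | 24.3% | 77% |
| 2% | 6 | 0.886 | 23.2% | 73% |
| 5% | 3 | 0.857 | 23.1% | 73% |
| 5% | 6 | 0.735 | 20.5% | 59% |

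These rows count drug use after week 24. If only use before week 24 counts (k = 2), q = 5% gives p' = 0.25×0.9025/(0.25×0.9025 + 0.75×0.95) = 24.1% and power 76.5%.

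**Step 5: both directions together.** Steps 3 and 4 each leave the other mechanism weak or absent. Take s_n = 0.85 and q = 5%.

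- k = 3 (s_b = 0.857): p' is 10.1% at a true 10% and 25.2% at a true 25%; type I error 5.0%, power 80.6%. The two effects cancel almost exactly.
- k = 6 (s_b = 0.735): at a true 25%, p' = 0.25×0.735/(0.25×0.735 + 0.75×0.85) = 22.4%; power 69%.

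**The case against.** The strongest reply is that 12.3.3 is loosely worded and the damage is hypothetical. Several parts of that reply stand.

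- **Timing.** A reader might infer that the plan deletes a patient at any time, even after 24 weeks of benefit, or reopens a stage 1 result already counted. No passage says so. Both follow only from the rule's silence on timing. Section 14 halts the trial to await the results of the first 18 patients and then takes the decision.
- **Analysis set.** The link from 12.3.3 to the primary CBR is inferred. Section 14 speaks of patients who enter and of the 43 patients, without naming a population.
- **Patients without benefit.** Treatment normally ends at documented progression (10.1.3). Survival follow-up begins at confirmed progression or new anticancer therapy (10.1.2). End-of-treatment assessments are to precede further therapy where possible (10.1, 10.1.4), and objective progression is to be sought after symptomatic deterioration (12.2.2.4.1). Therapy given after progression is not naturally read as concomitant. What remains is a prohibited drug given before documented progression, and nothing in the documents shows that 10% to 20% of patients without benefit fall there.
- **Size.** Every rate is assumed, and step 5 shows that the net effect can be almost nil.

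A reader might also note that 9.1.2 prohibits phosphorus absorbers while 9.4.3 directs their use, and conclude that about half the set would be deleted. That is a separate contradiction, which must be reconciled. The documents do not show that such protocol-directed use was meant to trigger this exclusion, and it is not relied on here.

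The reply does not remove the rule itself. The exclusion is stated and so is the replacement, and 12.3.2 shows that the authors wrote a time limit and an impact limit where they wanted them.

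**Conclusion.** The concern holds as a fault in a stated rule. As written, patients with a known outcome can leave the efficacy population and be replaced because of a post-baseline event that may be related to outcome or to time on study. The stated 5% error and 80% power are therefore not assured.

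This rests on two readings: that the 12.3.3 set supplies the 18 and the 43, and that a rule without a time limit has none. Nothing in the documents contradicts either.

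A firm claim that the trial is biased towards success, or towards failure, would go too far. The assumed rates give type I error of 7.5% to 11.8% in one direction and power between 77% and 59% in the other. Combined, they range from practically no distortion to a clear loss of power. Neither the sign nor the size is established.

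**What to change.** For the primary CBR, drop the second condition of 12.3.3 and do not replace these patients under 9.5. State in section 14 that they stay in the denominator of 18 and 43, scored as follows:

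- CR, PR or SD of at least 24 weeks documented before the prohibited treatment counts as benefit.
- Another anticancer treatment started before the endpoint is met counts as no benefit.
- Any other prohibited drug leaves the scored outcome unchanged.

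Report the set without these patients as a sensitivity analysis. Adding the time and impact limits of 12.3.2 to the exclusion would narrow the gap, but would still let an on-treatment event decide who is counted.

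The cost is a short edit to 12.3.3, 9.5 and 14, with no extra patients or data. Some patients with protocol deviations stay in the primary analysis, and the CBR may be slightly less favourable. If, for example, 5% of patients who would have had benefit start another anticancer treatment first, the rate scored is 0.25×0.95 = 23.75% and power is 75.3%; type I error stays below 4.8%.
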